2.5 Analysis of the primary objective

2.5.1 **Primary endpoint**

The primary endpoint is the time-averaged proportional change from baseline in NT-proBNP. Weeks 4 and 8 will be included in the analysis (primary analysis time point). The analysis of the primary endpoint will be based on the FAS.

2.5.2 Statistical hypothesis, model, and method of analysis

The primary hypothesis to be tested is the ratio of the geometric means of NT-proBNP (average of Weeks 4 and 8/baseline) for the sacubitril/valsartan and enalapril treatment groups are equal (H0) versus the ratio of the geometric means of NT-proBNP are not equal(Ha).

For NT-proBNP, the time-averaged proportional change from baseline in a logarithmic scale will be analyzed using an analysis of covariance (ANCOVA) model using data from Weeks 4 and 8 with treatment as a fixed effect factor and the logarithmic baseline biomarker value as a covariate.

The values from Weeks 4 and 8 will be averaged and the change from baseline in log-transformed NT-proBNP will be calculated as follows:

log (average post dose value) – log (baseline value)

The estimated treatment effect in terms of ratios of geometric means, based on the least-squares (LS) means from the model, and the corresponding two-sided 95% confidence intervals will be presented.

The geometric means (presented as a ratio to baseline) will be calculated by exponentially back transforming the LS means based on the ANCOVA model as follows:

exp (LS mean)

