Volume expansion and congestion during AHF leads to the synthesis and release of counter regulatory natriuretic peptides from the myocardium: A-type natriuretic peptide (ANP) responding predominantly to atrial distention and B-type natriuretic peptide (BNP) to ventricular wall stress. The precursor molecule of BNP is a propeptide (proBNP108) that when cleaved, results in the generation of the biologically active BNP and the release in the circulation of a biologically inert aminoterminal fragment called N-terminal prohormone of Brain Natriuretic Peptide (NT-proBNP). This fragment is a largely stable peptide that can be measured in serum. Both BNP and NT-proBNP are useful to aid the diagnosis or exclusion of HF (Yancy et al 2013). The PROTECT study was a small study (N=151) that demonstrated that NT-proBNP guided therapy was superior to standard of care in reducing total cardiovascular events, improved quality of life and impact on cardiac remodeling in patients with chronic reduced ejection fraction (Januzzi 2011). A larger on-going study is looking to evaluate whether treatment directed therapy based on NT-proBNP levels will provide benefit to patients compared to standard of care in patients with reduced ejection fraction (Felker 2014).

Patients developing an AHF episode are known to have markedly elevated levels of BNP and NT-proBNP, which are reduced following adequate treatment and normalization of their cardiac decompensation. In the RELAX AHF trial, it was shown that patients that have a higher NT-proBNP level during an AHF hospitalization have a worse prognosis (Metra et al. 2013). Therefore, it is important to evaluate therapeutic strategies that can lead to superior reductions in NT-proBNP in patients hospitalized due to an AHF episode.

Sacubitril/valsartan combination tablet is an orally available, first in class, combination of sacubitril, a neprilysin inhibitor, and valsartan, an angiotensin receptor blocker that targets complementary pathways, RAAS inhibition via an Angiotensin II receptor blockade and natriuretic peptide augmentation via neprilysin inhibition. This novel agent may also hold promise in modifying the poor outcomes currently observed after a hospitalization for AHF, especially in the initial high-risk post-hospitalization period.

Preliminary studies

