1.2 Rationale for protocol amendment

Amendment 2 (05Oct2017)

On the basis of blinded review of the projected aggregated (enalapril and sacubitril/valsartan treatment groups combined) rate of missing samples for NTproBNP, this rate exceeds the initial trial assumption of 10%. The sample size has been increased to 882 patients in order to preserve the originally intended power.

Given interest in the effect of sacubitril/valsartan on NTproBNP after titration to dose level 3, a secondary endpoint has been added.

Amendment 1 (28Jul2016)

The protocol inclusion criteria have been modified to be more closely aligned with clinical practice in the United States where patients with acute decompensated heart failure are often rapidly stabilized and transitioned from intravenous to oral diuretic therapy so as to move efficiently to outpatient care, with close follow-up. The protocol has been modified to include patients who are at least 24 hours from hospital presentation versus 48 hours. This change was instituted to allow sites to randomize stabilized patients who otherwise might be discharged earlier than 48 hours. In addition, the window of eligibility, which had been set at 5 days, has been extended to 10 days to permit inclusion of patients who have longer hospitalizations (e.g. due to initial diagnostic uncertainty).

Because a substantial proportion of patients who are stabilized with medical therapy for acute decompensation heart failure are asymptomatic with a systolic blood pressure that remains predominantly within the range of 100 - 110 mm Hg, the inclusion criterion regarding systolic blood pressure has been lowered to ≥ 100 mmHg. The SBP stabilization period was also changed from 24 hours to 6 hours because a 6 hour window is considered an adequate period of time to establish stability.

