1.1 Study design

This study will use a randomized, double-blind, double-dummy, active-controlled, parallel group design. Eligible patients hospitalized for acute decompensated heart failure (ADHF) will be randomized no earlier than 24 hours and up to ten days of presentation while still hospitalized. A total of approximately 882 patients randomized to sacubitril/valsartan or enalapril in a 1:1 ratio is planned with no stratification.

At the time of randomization, patients will have been stabilized, defined for this study as:

- Systolic blood pressure (SBP) \geq 100 mmHg for the preceding 6 hours prior to randomization; no symptomatic hypotension
- No increase (intensification) in intravenous (i.v.) diuretic dose within last 6 hours prior to randomization
- No i.v. inotropic drugs for 24 hours prior to randomization
- No i.v. vasodilators including nitrates within last 6 hours prior to randomization

All patients will need to meet all other inclusion and none of the exclusion criteria.

In order to provide for a necessary 36 hour washout of prior angiotensin converting enzyme inhibitors (ACEi) treatment prior to receiving sacubitril/valsartan (known as LCZ696 in prior trials), the supplied blinded study drug for those allocated to sacubitril/valsartan will be placebo only until the 3rd dose. Because the study is blinded, all patients, regardless of randomization arm, need to remain in the hospital for six hours after they have received their 3rd dose of study medication.

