Initial dose will be determined by the blood pressure at the time of randomization. Study treatment will be titrated to the Level #3 target doses of sacubitril/valsartan 97/103 mg (bis in diem/twice a day) bid and enalapril 10 mg bid. Titration will be based on blood pressure at the time of the visit. Dose adjustments will only be allowed if indicated per protocol defined safety/tolerability criteria and investigator judgement. At the end of the 8-week treatment period, all patients will need to have a 36 hour washout from study treatment prior to starting the open-label extension to ensure that the blinding of the core study is maintained. To facilitate this washout, patients should take their final dose of study drug on the morning of their week 8 visit and then begin open label sacubitril/valsartan after 36 hours in the evening of week 8 visit + one day. All patients will start open label treatment on sacubitril/valsartan at their final dosing level during double blind treatment. However, at an investigator's judgement, starting dose may be adjusted by one dose level up or down.

Eligible patients will be randomized no earlier than 24 hours after presentation at the hospital and no later than within ten days of admission, while still hospitalized, via interactive web

response system (IWRS) to one of the treatment arms. The investigator or his/her delegate will contact the IWRS after confirming that the patient fulfills all of the study entry criteria. The IWRS will assign a randomization number to the patient, which will be used to link the patient to a treatment arm and will specify which bottle from the centralized hospital supply the patient will be dosed for the first day and a unique medication number for the first package of investigational treatment to be dispensed to the patient.

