- Number of hospitalizations with primary diagnosis of HF within past 12 months not including index hospitalization
 - Number of hospitalizations categories $(0, 1, 2, \ge 3, \text{Not Applicable})$
- Total number of hospitalizations for any reason within past 12 months
- NYHA classification 30 days prior to index hospitalization (I, II, III, IV, Unknown)
- Ejection fraction (%)
 - Ejection fraction categories (>40%, >30% 40%, >20% 30%, ≤20%)
- Time from presentation to randomization (days)

Cardiovascular history

Cardiovascular history will be summarized. The following disease information will be collected:

- Hypertension (No, Yes, Unknown)
- Transient Ischemic Attack (TIA) (No, Yes, Unknown)
- Stroke (No, Yes, Unknown)
- Peripheral vascular disease (No, Yes, Unknown)
- Chronic renal insufficiency [eGFR <60 ml/min/1.73m² on testing >30 days prior to index hospitalization] (No, Yes, Unknown)
 - Chronic Kidney Disease (CKD) stage (CKD stage 3 [eGFR 30 59], CKD stage 4 [eGFR 15 29], CKD stage 5 [eGFR <15 or dialysis])
- Arrhythmia (No, Yes, Unknown)
 - Arrhythmia type (Atrial fibrillation, Atrial flutter, Supraventricular tachycardia, Ventricular tachycardia)
- Pacemaker/Implantable Cardioverter Defibrillator (ICD) (No, Yes, Unknown)
 - Device type (Pacemaker [conventional], Cardiac resynchronization therapy no ICD [CRT-P], Cardiac resynchronization therapy – with ICD [CRT-D], ICD only [single/dual], Other, Unknown)
- Moderate to severe valvular heart disease (No, Yes, Unknown)
 - Heart disease type (Mitral regurgitation, Aortic regurgitation, Aortic stenosis, Tricuspid regurgitation)
- Prior valvular heart surgery (No, Yes, Unknown)

• Valvular surgery type (Mitral, Aortic, Tricuspid, Pulmonic)

Non-Cardiovascular Medical History

Non-cardiovascular medical history and ongoing conditions will be summarized and listed. The summaries will be presented by primary system organ class (SOC), preferred term (PT) and treatment group for both double-blind and open-label patients. Non-cardiovascular medical history and ongoing conditions will be coded using Medical Dictionary for Regulatory Activities (MedDRA) terminology (v19.0 or later).

Surgeries and Medical Procedures

Surgeries and medical procedures will be listed, including the reason, start date and end date. Surgeries and medical procedures will be coded using MedDRA terminology (v19.0 or later).

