5.5 Statistical models

5.5.1 **Primary analysis**

The null hypothesis for the primary analysis is the ratio of the geometric means of NT-proBNP for the sacubitril/valsartan and enalapril group are equal. An ANCOVA model will be used. The model will have the time-averaged proportional change from baseline in a logarithmic scale be the dependent variable with treatment as a fixed effect factor and the logarithmic baseline value as a covariate. The general form for the ANCOVA model is:

$$y_{ij} = \mu + T_i + B(x_{ij} - \overline{x_i}) + E_{ij}$$

PROC MIXED in SAS will be used for the analysis. The LSMEANS option will be used with options of CL to output the confidence limits.

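### The primary ANCOVA adjusts only for log baseline NT-proBNP; adding time from presentation to randomization and prior ACEi/ARB use is an optional change with a small gain in precision.

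*SAP*

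**What the plan says.** SAP 2.5.2 specifies an ANCOVA of the log time-averaged change in NT-proBNP, "with treatment as a fixed effect factor and the logarithmic baseline biomarker value as a covariate". The model appendix (SAP 5.5.1) repeats this, "with treatment as a fixed effect factor and the logarithmic baseline value as a covariate", and protocol 9.4.2 has the same two terms.

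The timing of randomization is wide. SAP 1.1 states: "Eligible patients will be randomized no earlier than 24 hours after presentation at the hospital and no later than within ten days of admission". Protocol 1.2 records that Amendment 1 lowered the earliest time from 48 to 24 hours, and that "the window of eligibility, which had been set at 5 days, has been extended to 10 days". Nothing in the allocation balances this timing, since the "1:1 ratio is planned with no stratification".

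SAP 2.3.4 lists "Time from presentation to randomization (days" among the disease characteristics to be summarized. Prior ACEi/ARB use at hospitalization is a subgroup for the primary objective (SAP 2.2.1). Neither variable is a covariate in the primary model or in the supportive analyses of SAP 2.5.4.

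On the course of the biomarker, protocol 1.1 says that patients with an acute episode have "markedly elevated levels of BNP and NT-proBNP, which are reduced following adequate treatment and normalization of their cardiac decompensation". It gives no rate.

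**The concern.** Baseline NT-proBNP is sampled around the first dose, so it is taken on whichever hospital day the patient is randomized. If NT-proBNP is still falling then, the same reading can come from a patient sampled early or from one with a higher admission value sampled late. Their expected changes to Weeks 4 and 8 may differ, and log baseline alone cannot separate them. Any such variation stays in the error term.

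At stake is the width of the confidence interval for the primary treatment ratio, and so a little power. Both candidate covariates are fixed before randomization and already in the database.

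**Working it through.** **1. Reproduce the plan's sample size** (SAP section 3; protocol 9.7). Inputs: two-sided alpha 0.05, power 85%, 18% reduction, log-scale SD 0.85, 25% non-evaluable.

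- Effect on the log scale: δ = -ln(0.82) = 0.1985.
- Normal approximation: n per arm = 2 × (1.960 + 1.036)² × 0.85² / 0.1985², which rounds up to 330. Total 660 / 0.75 = 880.
- Noncentral t: 331 per arm. Total 662 / 0.75 = 882.7, against the stated 882. The figure reproduces.

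**2. Power as a function of what the covariates explain.** Evaluable per arm at 882: 882 × 0.75 / 2 = 330.75. If the added covariates explain a share R2 of the residual variance, the SD becomes 0.85 × √(1 - R2). Power then comes from the noncentral t with noncentrality δ / (SD × √(2/330.75)). The gain in evaluable patients is 661.5 × R2 / (1 - R2). R2 is an assumption; the documents do not give it.

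| Assumed R2 | Residual SD | Power | Equivalent extra evaluable patients |
|---|---|---|---|
| 0 (planned model) | 0.850 | 85.0% | 0 |
| 0.1% | 0.850 | 85.1% | 0.7 |
| 0.5% | 0.848 | 85.2% | 3.3 |
| 1% | 0.846 | 85.4% | 6.7 |
| 2% | 0.841 | 85.7% | 13.5 |
| 4% | 0.833 | 86.4% | 27.6 |

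For an observed ratio of 0.82, the 95% interval is 0.82 × exp(±1.96 × SD × √(2/330.75)). This gives 0.720-0.933 at R2 = 0 and 0.722-0.931 at R2 = 4%.

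**3. Which R2 is plausible for timing?** Assume the excess log NT-proBNP decays as D × 2^(-t/h), with t in days from presentation and half-life h. The change from day 5 to day 14 is then D × (2^(-5/h) - 2^(-14/h)). The bracket is 0.169 for h = 2 days and 0.332 for h = 4 days.

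- The plan takes 0.95 for enalapril and says its estimates come from day 5 to day 14 data. If 0.95 is that change, D = 0.0513 / 0.169 = 0.30 (h = 2) or 0.0513 / 0.332 = 0.15 (h = 4), where 0.0513 = -ln(0.95).
- R2 is about Var(D × 2^(-T/h)) / 0.85², where T is the day of randomization. Take T between 1 and 10 with a median of about 3, also an assumption. These values of D then give R2 of about 0.1% to 0.5%, and power of 85.1-85.2%.
- A total decline of 0.5 to 1.0 log units gives about 1% to 4%; the upper figure moves by about a point with the shape assumed for T. It also implies day 5 to day 14 ratios from exp(-0.5 × 0.169) = 0.92 down to exp(-1.0 × 0.332) = 0.72, all below the plan's 0.95.

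This step ignores whatever log baseline already captures.

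**4. Validity of the planned model.** In a simulation of 20,000 trials per setting (330 per arm, T uniform over 1 to 10 days, R2 of 5% and 10%), type I error was 4.9% and 5.1% without the time covariate, and 4.8% and 5.0% with it. The mean estimate under the alternative was -0.199 either way.

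**5. Chance imbalance.** If T is uniform over 1 to 10 days, its SD is 9/√12 = 2.60. The 95% range for the difference in arm means is ±1.96 × 2.60 × √(2/330.75), or about ±0.4 day.

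**The case against.** The strongest objection is that nothing is wrong with the planned analysis. Treatment is randomized, log baseline is the natural adjustment, and the SAP model matches protocol 9.4.2. Chance imbalance in an omitted covariate is already covered by the confidence interval. All of this stands.

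The mechanism is also less secure than it looks. A reader might infer that hospital day shows how much of the in-hospital fall is still to come. The documents do not support that. Protocol 1.1 gives direction only: levels "which are reduced following adequate treatment and normalization of their cardiac decompensation". Patients must first meet stability criteria on blood pressure and intravenous therapy, and protocol 1.2 mentions long stays caused by diagnostic uncertainty. Days since presentation are therefore not the same as days since effective treatment, and the log form for time is a convenience. For prior ACEi/ARB use, the documents give no figure for its prognostic value, so no separate gain can be credited to it.

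A reader might also infer that the trial is underpowered, because the planning data start at day 5 while randomization runs from day 1 to day 10. If 0.85 described a fixed day-5 start and varying start days added variance, power would be 84.4% at R2 = 2%. The documents do not say that 0.85 is such a figure, and they add that it is supported by PARADIGM.

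Finally, SAP 2.11 and 2.13 are not visible, so exploratory use of the time variable there cannot be excluded.

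The objection limits the size and severity of the point. It does not remove the case for adjustment, because the covariates are already collected and the cost is small.

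**Conclusion.** The point holds as an optional improvement of low severity. The primary model leaves out two pre-randomization variables that the trial already collects, and one of them varies over a wide, unstratified window. The planned analysis remains valid and unbiased, and 882 stands.

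The likely gain is small: from 85.0% to about 85.1-86.4% power for an assumed partial R2 of 0.1% to 4%. The low end is the better guess if the plan's 0.95 describes the day 5 to day 14 change and days count from presentation. The interval limits move only in the third decimal place. Larger gains, or a claim of bias, would need a rate of fall or a correlation that the documents do not contain.

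**What to change.** Before unblinding, add log(time from presentation to randomization) and prior ACEi/ARB use (yes/no) as fixed covariates in the primary ANCOVA (SAP 2.5.2 and 5.5.1) and in the Week 8 NT-proBNP ANCOVA (SAP 2.7.2). Keep the current two-term model as a supportive analysis in SAP 2.5.4, and record the change in SAP section 4.

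The cost is SAP wording, two degrees of freedom among about 660 evaluable patients, and a primary model that departs from protocol 9.4.2. Because eligibility depends on the time from presentation, that variable should be nearly complete. If the sponsor prefers not to depart from the protocol model, the adjusted model could be the named supportive analysis instead. The primary test would then gain nothing.

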9.4.2 Statistical model, hypothesis, and method of analysis

The primary hypothesis to be tested is that the ratio of the geometric means of NT -proBNP (average of Weeks 4 and 8/baseline) for the sacubitril/valsartan and enalapril groups are equal (H0) versus the ratio of the geometric means of NT-proBNP are not equal (Ha).

For NT-proBNP, the time-averaged proportional change from baseline in a logarithmic scale will be analyzed using an analysis of covariance (ANCOVA) model using data from Weeks 4 and 8 with treatment as a fixed effect factor and the logarithmic baseline biomarker value as a covariate The estimated treatment effect in terms of ratios of geometric means, based on the least-squared means from the ANCOVA model, and the corresponding two -sided 95% confidence intervals will be provided. Baseline is Week 0.

The change from baseline log-transformed NT-proBNP will be calculated as log (post-dose value) – log (baseline value). Geometric means (presented as a ratio to baseline) will be calculated by exponentially back-transforming the LS means based on the ANCOVA model.

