9.4.3 Handling of missing values/censoring/discontinuations

The analysis will be performed based on all available data in the FAS and based on likelihood method with an assumption of missing at random for missing data.

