2.5.3 Handling of missing values/censoring/discontinuations

The analysis will be performed based on all available data in the FAS and based on likelihood method with an assumption of missing at random for missing data.

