2.7.2 Statistical hypothesis, model, and method of analysis

For NT-proBNP at Week 8, a proportional change from baseline in a logarithmic scale will be analyzed using an ANCOVA model with treatment as a fixed effect factor and the logarithmic baseline biomarker as a covariate. The estimated treatment effects in terms of ratios of geometric means, based on the LS means from the ANCOVA model, and the corresponding two-sided 95% confidence intervals will be provided. Baseline is Week 0. Week 4 will be used if the Week 8 value is missing.

The incidence of symptomatic hypotension up to Week 8 will be calculated by treatment group. The relative risk (sacubitril/valsartan vs. enalapril) and the 95% confidence interval will also be presented. Similarly, the incidence of hyperkalemia, all angioedema, and positively adjudicated angioedema during the 8 week double-blind phase and the relative risk (sacubitril/valsartan vs. enalapril) will be summarized. Additionally, medication change, lowest documented systolic blood pressure and lowest documented diastolic blood pressure will be summarized by treatment group for symptomatic hypotension. The highest potassium value documented for hyperkalemia will also be summarized by treatment group.

For biomarkers including BNP, BNP to NT-proBNP ratio, NT-proBNP to BNP ratio, hs-Troponin T, UcGMP, and UcGMP to urinary creatinine ratio, the time-averaged proportional change from baseline in a logarithmic scale will be analyzed using an ANCOVA model using data from Weeks 4 and 8 with treatment group as a fixed effect factor and the logarithmic baseline biomarker value as a covariate.

Similar to the primary endpoint, the values from Weeks 4 and 8 will be averaged and the change from baseline will be calculated.

The estimated treatment effect in terms of ratios of geometric means, based on the LS means from the model, and the corresponding two-sided 95% confidence intervals will be presented. The geometric means (presented as a ratio to baseline) will be calculated by exponentially back transforming the LS means based on the ANCOVA model.

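### The one-record ANCOVA on the Week 4 and 8 average does not give the likelihood, missing-at-random handling that SAP 2.5.3 states for patients with one week missing, and no visible text says how their average is formed.

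*SAP*

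**What the plan says.** - **Response.** SAP 2.5.2: "The values from Weeks 4 and 8 will be averaged and the change from baseline in log-transformed NT-proBNP will be calculated as follows". The formula is the log of the average post-dose value minus the log of baseline.
- **Model.** SAP 5.5.1: "The model will have the time-averaged proportional change from baseline in a logarithmic scale be the dependent variable". The only other terms are treatment and log baseline. PROC MIXED with LSMEANS is named; no visit term and no within-patient covariance is.
- **Missing data.** SAP 2.5.3 says the analysis is "based on all available data in the FAS and based on likelihood method with an assumption of missing at random". Protocol 9.4.3 has the same statement: "based on likelihood method with an assumption of missing at random for missing data".
- **Protocol model.** Protocol 9.4.2 uses data from Weeks 4 and 8, and says: "The change from baseline log-transformed NT-proBNP will be calculated as log (post-dose value") minus the log of baseline. It does not say to average the raw values before taking the log.
- **Nearby rules for a missing week.** SAP 2.7.2, for the Week 8 secondary endpoint: "Week 4 will be used if the Week 8 value is missing". In SAP 5.6, deviation O05 (a missing sample at baseline, Week 4 or Week 8) excludes the patient from the Per-Protocol Set (PPS) only.
- **Evaluability.** SAP 2.5.4 plans a summary of patient evaluability by arm without defining it. Protocol 9.7 and SAP Section 3 allow for 25% missing or non-evaluable samples.

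**The concern.** SAP 2.5.3 states a property that the model in 2.5.2 and 5.5.1 does not have. A likelihood analysis under missing at random earns its value when both weeks enter as separate outcomes, so that a patient's Week 4 value informs the missing Week 8 value. Once the two weeks are collapsed into one number, that link is gone. The patient is either left out or entered as if the single week were the average, and the SAP does not say which.

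This is the primary estimate. Amendment 2 reports that the projected rate of missing NT-proBNP samples exceeds the 10% first assumed, and the trial was enlarged for 25%. One-week patients may therefore not be rare. Two programmers could build different primary datasets from the same text, and a rule chosen after unblinding would be open to question.

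**Working it through.** **1. The plan's own figure.** Inputs from Protocol 9.7 and SAP Section 3: ratio 0.82, SD 0.85 on the log scale, two-sided alpha 0.05, power 85%, 25% non-evaluable.

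n per arm = 2 × (1.960 + 1.036)² × 0.85² / (ln 0.82)² = 2 × 8.98 × 0.7225 / 0.0394, or 330 after rounding up. Then 660 / 0.75 = 880. The t-based version gives 331 per arm and 662 / 0.75 = 882.7. The planned 882 reproduces, and nothing here changes it.

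**2. What a one-record fit protects against.** With one row per patient and no repeated or random effect, PROC MIXED gives the least-squares ANCOVA. That is a likelihood fit. In general it is protected only against missingness that depends on treatment and baseline alone. Missing at random given the patient's other post-dose week is not covered.

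**3. The two possible readings.**
- *Both weeks required.* Valid if, given treatment and baseline, missingness does not depend on the observed week's value.
- *Available week used.* No shift when the effect is constant and dropout works the same way in both arms. It shifts if the effect differs between Weeks 4 and 8, even under completely random loss, or if dropout depends on Week 4 differently by arm.

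**4. How many patients.** The documents do not say. Taking 25% as an assumed Week 8 loss and assuming 10% Week 4 loss:
- Independent loss: one week only = 0.9 × 0.25 + 0.1 × 0.75 = 0.30, and 882 × 0.30 = 265.
- Nested loss (everyone missing Week 4 also misses Week 8): 0.25 − 0.10 = 0.15, and 882 × 0.15 = 132.

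**5. Available week, by hand.** Assume random independent loss and an effect growing from 0.92 at Week 4 to 0.731 at Week 8, for which the full-data log-of-average ratio is 0.824. Shares: both weeks 0.675, Week 4 only 0.225, Week 8 only 0.075, total 0.975.

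(0.675 × ln 0.824 + 0.225 × ln 0.92 + 0.075 × ln 0.731) / 0.975 = (−0.1307 − 0.0188 − 0.0235) / 0.975 = −0.1774

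The shift is −0.1774 − (−0.1936) = 0.0162, and 0.82 × exp(0.0162) = 0.833. With SE = 0.85 × √(4/860) = 0.058, this is 0.28 SE.

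**6. Simulation.** 882 patients, 2,000 trials per scenario. From the documents: SD 0.85, enalapril ratio 0.95, true ratio 0.82. Assumed: baseline explains 10% of variance, Week 4-to-8 correlation 0.6, the independent loss of step 4, and a logistic slope of Week 8 dropout on the Week 4 change (per SD, enalapril / sacubitril-valsartan). Each result is scaled to a full-data value of 0.82.

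| Assumed pattern | Available week | Both weeks | Two-visit likelihood |
|---|---|---|---|
| Constant effect, slopes 1/1 | 0.820 | 0.836 | 0.820 |
| Constant effect, slopes 1/0.5 | 0.812 | 0.897 | 0.820 |
| 0.92 then 0.731, random loss | 0.833 | 0.820 | 0.820 |
| Same, 32% Week 8 loss | 0.840 | 0.820 | 0.820 |

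Nested loss moves the available-week results by at most about 0.003.

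**7. How firm these are.** In SE units the available-week shifts are ln(0.82/0.812) / 0.058 = 0.17 and ln(0.833/0.82) / 0.058 = 0.27. Harsher assumptions go somewhat further: 0.842 when the reversed arm difference in dropout is stacked on the growing effect (0.46 SE), and 0.805 in a separate simulation with slopes of 1 against 0 (0.32 SE). The both-weeks figure is far less stable. For slopes 1/0.5 it falls from 0.897 to 0.876 when loss is made equal in the two arms. With dropout also centred within arm, it is 0.840 for slopes 1/0.8 and 0.820 for 1/1. The separate simulation ranged from 0.73 to 0.95. The two-visit model stayed at 0.819 to 0.821 throughout.

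**The case against.** The strongest reply is that the two readings are not equally open. SAP 2.5.3 speaks of all available data, and O05 removes one-week patients from the PPS but leaves them in the Full Analysis Set (FAS). If the FAS analysis already required both weeks, the Week 4 and Week 8 part of O05 would remove nobody further from the PPS analysis of this endpoint. This stands. The text leans to the available week, where the shift is small. It is still only a lean, and substituting the observed week for the average is not missing-at-random likelihood handling.

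Other points that stand in part:
- A reader might infer that the protocol prescribes a repeated-measures model from which the SAP departs. It does not: Protocol 9.4.2 states the hypothesis on the average and lists only treatment and log baseline. A two-visit model is compatible with its wording but not specified by it.
- A growing effect is speculative. Amendment 2 does say "Given interest in the effect of sacubitril/valsartan on NTproBNP after titration to dose level 3, a secondary endpoint has been added". However, the only time course against enalapril in the documents is flat (26% at Week 4, 25% at Month 8; Protocol 9.7), and the titration goal is Week 2 (Protocol 5.5.4).
- The 25% is a missing or non-evaluable rate for the sample size. Using it as a Week 8 loss rate is an assumption, and the 32% has no source in the documents.
- The by-visit ANCOVAs, the evaluability summary and the PPS analysis would help reveal a problem. They do not correct the primary estimate.

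**Conclusion.** The point holds as a mismatch and an omission in the primary analysis. For patients with one of the two weeks, the specified model does not deliver the handling that SAP 2.5.3 states, and no visible text gives the rule for their average. It should be fixed.

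On the better-supported available-week reading, the likely effect is small: about 0.81 to 0.83 for a true 0.82, under 0.3 SE, and none with a constant effect and common dropout. Only harsher assumed patterns exceed that.

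A reader might infer that the primary estimate is seriously biased, for example near 0.90. The documents do not support this. It needs the less-supported both-weeks reading, a twofold arm difference in how dropout depends on Week 4, and a particular calibration. Nor do they support a claim of lost power, since 882 reproduces and the share of one-week patients is not given.

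**What to change.** Before unblinding:
- Analyse log(visit value) minus log(baseline) at Weeks 4 and 8 in a repeated-measures likelihood model with treatment, visit, treatment-by-visit, log baseline, log baseline-by-visit and unstructured covariance.
- Take the equally weighted mean of the two treatment contrasts, back-transformed, as the primary estimate, and list the change in SAP Section 4.
- Keep the log-of-average ANCOVA as a sensitivity analysis, with a stated rule for one missing week.

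If the one-record ANCOVA stays primary, state the one-week rule, define 'evaluable' in SAP 2.5.4, and reword 2.5.3 so that it does not claim handling the model does not provide. The biomarker analyses in SAP 2.7.2 and 2.7.3 share the averaging and the missing-data statement and need the same edit.

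The cost is SAP wording and a few lines of code, with no new data. The one downside is that the summary becomes the mean of the logs instead of the log of the average. The two agree for a constant effect; with 0.92 at Week 4 and 0.731 at Week 8 they are 0.820 and 0.824.
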